1.5. Aromatase Inhibitors

1.5.1. Pharmacokinetic Considerations of the Combination Therapy

The pharmacokinetics and metabolism of letrozole and anastrozole are well understood¹⁰. A key question for us is whether we anticipate any interactions with AZD4547. Letrozole with continuous oral dosing reaches a steady state at 2-6 weeks. The drug is cleared through hepatic metabolism via CYP3A4 and CYP2A6 and subsequent urine clearance. Anastrozole reaches a steady state after 7 days and is 40% plasma protein bound. It is also metabolised in the liver and cleared via the kidneys. It has no effect on CYP2A6 but can inhibit CYP1A2 and CYP2C8 albeit at higher concentrations (2 logs) than clinically used. AZD4547 binding to human serum albumin and to human α 1-acid glycoprotein was 93.2% and 69.6% respectively. One of the principal metabolites formed by human hepatocytes was found in the rat, but other human metabolites were not formed in significant amounts in any non-clinical species. CYP3A4, CYP3A5 and CYP2D6 are likely to be responsible for the metabolism of AZD4547 in vivo, although CYP1A1 turnover may be important in smokers. AZD4547 produced competitive inhibition of CYP3A4/5 using testosterone as the probe substrate, but not with midazolam, and it was also shown to be a time dependent inhibitor of the same isozymes.

From the above, we do not anticipate any problems with the combination of anastrozole and AZD4547. However, there is a small possibility that letrozole and AZD4547 may interact through one of their common metabolising enzymes CYP3A4. Nevertheless, AstraZeneca have in house data showing that other drugs using this pathway are unaffected by AZD4547 suggesting that this issue may not be clinically relevant. On this basis, the safety run-in part of the trial has been designed to start using the pharmacologically active, tolerated, dose defined from the currently running Phase I AZD4547 trial with the usual clinical dosing used for either anastrozole or letrozole.

1.6. Rationale

There is an increasing body of evidence implicating FGFs such as FGF-2 and their receptors in cancer biology, whereby these growth factors/receptors drive cancer cell proliferation, invasion, and

survival as well as facilitating neoangiogenesis. More recently, it has become clear that FGF-2 and its receptors FGFR1 and FGFR2 can also induce resistance to multiple chemotherapeutic agents in several cancer types. Consequently, there has been considerable interest in developing selective FGFR inhibitors. The most widely used FGFR inhibitor in preclinical studies has been PD173074. We have shown this to be selective (like AZD4547) and active in blocking the growth of multiple lung cancer cell lines in vitro as well as able to block SCLC xenograft growth in vivo¹¹ (and data not shown). Moreover, PD173074 blocks chemoresistance in vitro and enhances the effects of chemotherapy in vivo. There is no reason to believe that AZD4547 would behave differently and our preliminary data confirms this in lung cancer cells.

1.6.1. Rationale for use in Breast Cancer

Ectopic over expression/activation of FGFR1 in mammary cells leads to increased proliferation and invasiveness, reduced survival and cell transformation¹² and expression of an FGFR1 transgene in mice caused mammary alveolar hyperplasia and invasive lesions¹³. In the SUM44, MDA-MB-134 and CAL120 cell-lines FGFR1 gene amplification correlates with high levels of FGFR expression and activation of downstream signaling pathways including pErk and pAkt pathways^{4,14}. The MDA-MB-134 cell-line is highly dependent upon FGF-ligand for growth and survival and very sensitive to growth inhibition by AZD4547 (IC50 =15nM). Exposure of SUM44 cells to FGF induces resistance to the growth inhibitory effects of tamoxifen and in both this cell-line and CAL120 down regulation of FGFR1 sensitizes to the growth inhibitory effects of tamoxifen treatment⁴. These data suggest that inhibition of FGFR1 can arrest the growth of mammary cells by both endocrine-dependent and endocrine-independent mechanisms. This together with the data presented previously provides a rationale for why AZD4547 should be tested in combination with AIs such as anastrozole and letrozole to see whether it can reverse resistance to these AIs. In addition, one of the key questions as FGFR inhibitors like AZD4547 are developed, is whether amplification of FGFR1 is really necessary to see benefit from this class of agent. Our pre-clinical data suggests that such amplification may not be necessary and this study will therefore also test this hypothesis.

1.6.2. Rationale for Revised Phase IIa Study Design

When this study was originally conceived, the standard of care for post-menopausal women with ER positive advanced breast cancer included letrozole or anastrozole therapy. Once this therapy failed, many women were then given exemestane alone before progressing to chemotherapy. However, the recent results of the Bolero trial¹⁵ and other studies have changed the landscape and currently, many women are now being offered exemestane together with the rapalogue everolimus. This is clearly efficacious but also considerably more toxic than exemestane alone. Consequently, whether this will remain the next line of therapy following resistance to letrozole and anastrozole is very unclear particularly since a number of other novel agents are being studied in this disease setting. Therefore, in discussion with the UK breast community, the Trial Steering Committee (TSC) and Trial Management Group (TMG) felt that the most appropriate design was a simple non-randomised single arm design in which the central hypotheses of whether AZD4547 can re-establish response to either letrozole or anastrozole will be tested and whether FISH6 FGFR1 amplification is necessary for this benefit; there will also be an ongoing appraisal of safety and tolerability.

1.6.3. Rationale for AZD4547 Dose and Schedule (Phase IIa)

On completion of the DLT review period, the Safety Review Committee (SRC) reviewed all available safety data from both cohorts in the safety run-in part of the study and made the recommendation that 80mg bd AZD4547 one week on/one week off + NSAID combination will be carried forward to the Phase IIa part of the study.

1.6.4. Risk – Benefit Assessment

Potential Benefits

Dysregulation of the FGFR pathway is observed in a variety of cancers, due to gene amplification, translocations or mutations. Non-clinical data suggests that inhibition of FGFR mediated signalling can result in an anti-proliferative and/or proapoptotic activity and may also have an anti-angiogenic effect.

Potential Risks and their Management

Ocular Toxicity

In the clinical studies conducted to date the adverse events reported regarding the anterior aspect of the eye (dry eyes, blurred vision, conjunctivitis and keratitis) are consistent with the pathological changes that were seen pre-clinically. It is anticipated that patients will report any visual disturbances or discomfort relating to the eye in advance of any significant pathology such as ulceration occurring. The decision to continue on study treatment if mild corneal changes in the eye examination are observed will be left to the Investigator's discretion, since a patient may indicate a wish to tolerate minor discomfort if there is perceived clinical benefit from the therapy. A patient should be immediately withdrawn from study treatment if corneal ulceration occurs, and appropriate expert ophthalmologic consultation should be initiated.

Retinal pigmented epithelium detachment (RPED) has been identified in clinical studies with AZD4547 (45 occurrences as of 04 June 2014). Patients with conditions pre-disposing to the development or re-occurrence of RPED will be excluded from participation in the study. In order to detect this, patients will have a baseline ophthalmologic examination (including OCT scan) prior to initiation of study treatment and approximately monthly for the first 3 months. Thereafter, patients continuing the study treatment will have a full ophthalmological review every 8 weeks (+/- 1 week) until permanent discontinuation of AZD4547. At any other time, abnormal visual symptoms or signs will trigger a full ophthalmological review.

Mineralisation, Particularly in the Heart

The cardiac mineralisation identified in both non-clinical species is thought to be as a direct consequence of elevated serum phosphate levels. The increase in phosphate levels are thought to be pharmacological as a consequence of inhibition of FGF23 modulated phosphate homeostasis in the kidney. In the dog, the increase in phosphate level occurred prior to mineralisation, and at lower doses where no mineralisation occurred. Mineralisation was of low incidence, and was not present following 4 weeks off dose. The clinical studies to date have confirmed the pre-clinical finding of increases in serum phosphate and following review of the data hyperphosphataemia is considered to be an expected event in patients treated with AZD4547. There have been no reports, and no evidence of any soft tissue, including cardiac, mineralisation clinically. However based upon the presumption that increases in phosphate precede mineralisation, patients will be excluded from the study if they have phosphate or calcium levels above the upper limit of normal prior at time of entry. Serum phosphate and calcium are included in the standard clinical chemistry safety bloods which will be assessed on a regular basis. Any patient who experiences a doubling of phosphate from baseline or a corrected calcium:phosphate product >4.5 mmol/L should have phosphate chelation therapy initiated with a non-calcium containing agent, and weekly clinical chemistry assessments performed until resolution of the parameter to below the intervention limit. Investigators must seek appropriate specialist medical consultation (renal or metabolic) to advise on the prescription and titration of phosphate chelation agents, and to raise the patients' awareness of low phosphate diets.

It is likely that mineralisation occurring within the heart will result in functional changes prior to any gross structural changes being apparent by specific imaging technology. Therefore patients will have regular troponin I or troponin T measurements at the same time as the clinical chemistry safety blood measurements. In addition ECGs and MUGA/echocardiograms will be assessed regularly as detailed in the study plan while the patient is on study treatment in order to identify functional changes. The protocol includes standard exclusion criteria for unstable cardiac conditions and risk factors for QTc prolongation.

Renal Toxicity

In clinical studies of AZD4547 in advanced cancer populations there have been 8 renal SAEs in 7 patients. Each case may have an alternative explanation for the events, such as presence of a renal tumour, adrenal metastases, advanced cancer, and a history of listhesis. Analysis of the laboratory values for serum creatinine showed that 30% of patients have had an abnormal serum creatinine value while taking AZD4547 or during the follow-up period. Of these, 19 patients had an improvement in the serum creatinine level when AZD4547 was stopped either temporarily or permanently.

Although there are multiple alternative explanations for the observed elevated creatinine levels (such as advanced cancer patients with disease progression, nephrotoxic concomitant medications, or a history of renal failure) there appears to be a pattern in many patients where the phosphate rises in tandem with serum creatinine. The magnitude of change is not the same but the general trend upwards or downwards is matched. Intermittent dosing schedules show the effect more clearly, and the pattern can be seen in patients with normal serum creatinine values, as well as those whose creatinine rises above the upper limit of normal.

All patients should be closely monitored for any signs of impaired renal function. Patients should be excluded from the study if they have serum creatinine >1.5 times the upper limit of normal concurrent with creatinine clearance <50 mL/min (measured or estimated by Cockcroft and Gault formula). Serum creatinine and blood urea nitrogen will be included in the standard clinical chemistry safety bloods and will be assessed on a regular basis.

Bone Turnover

Histopathological changes in bone structure have been identified in the rat but not the dog. Similar bone changes have been reported in the literature following administration of another FGFR inhibitor to rats, and have been considered due to a pharmacological effect on growing bones. Patients born with mutations in FGFR genes develop a range of skeletal disorders during childhood such as osteoglyphonic dysplasia, Apert syndrome and hypochondroplastic dwarfism. Only patients over the age of 25 will be permitted to enter the study, in order to exclude individuals who have not completed maturation of their skeleton. Bone adverse events will be reviewed on a case-by-case basis as it is not possible to provide specific stopping criteria given the background of extensive metastatic disease seen with the advanced cancer patient population, which might result itself in pathological fractures and bone pain.

Mouth-related conditions

Events of ageusia, dysguesia, stomatitis/oral mucositis and xerostomia have been reported in the clinical studies to date. In cases of stomatitis particular attention should be given to prophylaxis, maintaining a high standard of oral hygiene with the regular use of antibacterial mouthwashes during the study. Saline nasal sprays may help nasal mucosal dryness and so reduce the incidence of epistaxis.

Dermatological Toxicity

There have been a number of events reported in patients receiving treatment with AZD4547 involving the skin and associated appendages. These include events of dry skin, alopecia, hair changes, trichomegaly and changes to the nails and nail beds.

Diarrhoea

Diarrhoea has been commonly reported in patients receiving AZD4547 across all studies, the majority of which have been non-serious and CTCAE Grade 1. Diarrhoea is therefore considered as an expected event in patients treated with AZD4547. Patients have responded to symptomatic treatment, for example with loperamide.

Neutropenia

Neutropenia and febrile neutropenia are common risk factors for cancer patients receiving chemotherapy treatment. A review of data for patients enrolled in AZD4547 clinical studies has not identified any dose relationship with neutropenia and indicates most events are CTCAE Grade 1 or Grade 2. However, events of CTCAE Grade 4 neutropenia have been reported and were associated with febrile events with the possibility of infection, treatment with antibiotics was given. One patient who died had febrile neutropenia but the investigator considered the patient died as a result of disease progression. Two CTCAE Grade 1 AEs were considered by the investigator to be related to treatment with AZD4547. Two SAEs with element of neutropenia have been reported (1 in Study D2610C00003 and 1 in an Investigator-Sponsored Study); however, these were not considered to be related to AZD4547 treatment.

Any AE of neutropenia should be managed as deemed appropriate by the investigator with close follow up and interruption of study drug if CTCAE Grade 3 or worse neutropenia occurs. If a patient develops febrile neutropenia, study treatment should be stopped and appropriate management including granulocyte-colony stimulating factor should be given according to local hospital guidelines.

Increases in Transaminases

Increases in transaminases have been reported in the clinical studies to date and following review of the data are considered to be expected events in patients treated with AZD4547. Most of these increases were CTCAE Grade 1 or Grade 2. There was no clear relationship between the dose of AZD4547 and the incidence or severity of the increase in transaminases.

Intermittent dosing schedules have allowed examination of the effect of dechallenge and rechallenge with AZD4547, and while there was some evidence of an effect with AZD4547 in a few patients, overall, there was little difference in the data obtained from dosing with continuous or intermittent schedules. Liver function test abnormalities were most common in patients with liver metastases and in patients with progression of their underlying cancer; multiple concomitant medications in these patients is also a confounding factor.

Studies of AZD4547 include regular measurements of ALT, AST and other hepatic biochemistry parameters. All patients should be closely monitored for any signs of liver toxicity.

Asthenic Conditions

Literature for multi-targeted kinases suggests there may be an association between asthenic events and the use of FGFR and VEGF inhibitors; however, it is difficult to suggest there is an association directly with FGFR inhibitors.

There is also a suggestion from pre-clinical findings that FGF may modulate some of the metabolic processes such as FGF-19 (ligand for FGFR4) and FGF21 (ligand for FGFR 1, 2, 3, and 4) that can

regulate glucose, lipid, and energy metabolism and cause changes in energy expenditure; this may provide a mechanism for why asthenic events occur with FGFR inhibitors.

Preliminary findings from the data analysed within the AZD4547 clinical studies shows an incidence of asthenic reported terms of approximately 50% within the most frequently prescribed schedule of 80 mg bd continuous cohorts. There is not a dose response for asthenic AEs occurring at higher doses in the continuous schedule. Findings are inconsistent, the proportion of AEs are less severe and frequent in the 120 mg and 200 mg cohorts in comparison with those found in the 20 mg to 160 mg cohorts.

The data for asthenic events for intermittent schedules of 80 mg bd (1 week on/1 week off and 2 weeks on/1 week off) shows an incidence of approximately 45% to 50% and approximately 50% for patients receiving 80 mg continuously. There is also >50% incidence of asthenic conditions reported in the higher dosing cohorts in Study D2610C00001 and D2610C00002.

Across all the studies the time to onset for asthenic conditions overlaps amongst the varying dosing cohorts. This makes it difficult to suggest a causal relationship as the time to onset is not reduced in the higher dosing cohorts and intermittent schedules where patients are off drug for 1 week. Confounding factors such as disease progression, low haemoglobin values, comorbidities such as hypothyroidism, chronic obstructive pulmonary disease, infections and multiple concomitant medications (opiates, antihistamines, anti-hypertensive, anti-nausea) are alternative explanations for asthenic events, but no single factor can explain all cases. Common treatable causes of asthenic conditions (e.g., iron, vitamin B12 or folate deficiencies and hypothyroidism) should be investigated in patients with asthenia, fatigue or malaise.

Reproductive Organs

No reproductive toxicology or teratogenic studies have been conducted with AZD4547 to date, and it is unknown whether the drug is excreted in human milk. This study is being conducted in postmenopausal women only and so this is not considered a relevant risk in this study.

Possible Drug Interactions

AZD4547 is a substrate of CYP3A4 and CYP2D6 therefore use of inhibitors/inducers of these isoforms will be excluded from 2 weeks prior to the first dose of AZD4547 and for the duration of study treatment. CYP1A1, an isoform highly inducible by cigarette smoking, is also capable of metabolism of AZD4547 and may lead to lower exposures in smokers, therefore smoking status will be recorded as part of the demographic information for all participating patients. AZD4547 shows weak competitive inhibition of CYP3A4 and is also a time-dependent inhibitor of this isoform. This may lead to reduced metabolism (and increased exposure) of any co-administered drugs that are significantly cleared via this pathway. Concomitant use of medicines significantly metabolised by CYP3A4 will be contraindicated during the course of the study. Use of other agents less significantly metabolised will be permitted with caution if considered clinically indicated for the welfare of the patients, and patients will be closely monitored for possible drug interactions.

Overall Benefit-Risk Assessment

In the advanced cancer setting that has been chosen for this study, prolonged survival rates are very low and there is a large unmet clinical need for novel therapeutic agents.

Although there can be no certainty of clinical benefit to patients, non-clinical data with AZD4547 support the hypothesis that FGFR inhibition may be a valid target for the treatment of tumours driven via this pathway. The non-clinical safety profile has not identified any risks that would preclude

investigation in this setting, and monitoring is in place for those risks deemed to be most likely or serious.

Investigation of AZD4547 in this patient population is justified, based upon the non-clinical safety profile, the limited life expectancy due to malignant disease, and the strength of the scientific hypothesis under evaluation. Thus the benefit/risk assessment for this study supports the oral administration of AZD4547 together with anastrozole or letrozole to patients with advanced cancer, according to the proposed study design.

2. STUDY OBJECTIVES AND ENDPOINTS

2.1. Primary Objectives

Safety run-in

- To assess the safety and tolerability and determine the dose of AZD4547 to be used in combination with a standard dose of anastrozole for the phase IIa part of the study
- To assess the safety and tolerability and determine the dose of AZD4547 to be used in combination with a standard dose of letrozole for the phase IIa part of the study

Phase IIa

- To assess the efficacy of AZD4547, based on the change in tumour size at 12 weeks (or progression if prior to week 12), when used in combination with either anastrozole or letrozole in ER positive breast cancer patients who have progressed on treatment with either anastrozole or letrozole in any setting.

2.2. Secondary Objectives

Safety run-in

- To assess the pharmacokinetics (PK) of anastrozole or letrozole when given alone compared to in combination with AZD4547
- To describe the PK of AZD4547 when given in combination with anastrozole or letrozole

Phase IIa

- To assess the efficacy of AZD4547 in combination with anastrozole or letrozole as measured by change in tumour size at 6 weeks, 20 weeks, then every 8 weeks, as per study plan.
- To assess the efficacy of AZD4547 in combination with anastrozole or letrozole as measured by the tumour response (RECIST criteria) at 6 weeks, 12 weeks, then every 8 weeks, as per study plan.
- To assess the efficacy of the study treatment as measured by the objective response rate (ORR) at 6 weeks, 12 weeks, then every 8 weeks, as per study plan.
- To assess the efficacy of the study treatment as measured by progression-free survival (PFS)
- To assess the safety and tolerability of AZD4547 in combination with anastrozole or letrozole

2.3. Primary Endpoints

Safety run-in

- Safety and tolerability as assessed by DLTs

Phase IIa

- Change in tumour size at 12 weeks (or progression if prior to week 12)

2.4. Secondary Endpoints

Safety run-in

- PK parameters of anastrozole or letrozole when given alone and in combination with AZD4547
- PK parameters of AZD4547 when given in combination with anastrozole or letrozole
- Safety and tolerability as assessed by AE

Phase IIa

- Change in tumour size at 6 weeks, 20 weeks, then every 8 weeks, as per study plan
- Tumour response RECIST criteria with 4 categories: complete response (CR), partial response (PR), stable disease (SD), progressive disease (PD)
- Objective response rate (ORR) with 2 categories: CR, PR, SD versus PD.
- Progression-free survival (PFS) is time from study entry to PD (RECIST)

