- Objective response rate (ORR) with 2 categories: CR or PR, SD or PD
- Progression-free survival (PFS) is time from study entry to PD (RECIST)

Exploratory Endpoints:

- To collect and store plasma, serum and archival tumour samples or paired tumour biopsies, and analyse surplus blood or tissue, if available, for potential future exploratory research into factors that may influence development of cancer and/or

response to AZD4547 (where response is defined broadly to include efficacy, tolerability or safety)

- To investigate PK/PD relationships including serum FGF23, serum phosphate levels, serum FGF-2 (Safety run-in only)
- To analyse a range of oncology biomarkers, which may correlate with drug response
- To investigate the association between FGFR1 FISH score and the above primary and secondary efficacy endpoints (Safety run-in only)

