5.2.21. Tumour Assessments (Phase IIa only)

Tumour assessments will be performed using CT or MRI scans of the chest, abdomen and pelvis. The same method used for assessment at baseline must be used at all subsequent time points.

Tumour assessment will include: if disease is measurable or non-measurable (at least one lesion must be measurable), date of assessment, imaging method used, site (breast, lung, liver, pleural effusion, local lymph nodes, distant lymph nodes, bone, brain or other site), longest diameter of each target lesion and sum of longest diameters for all target lesions.

Patient response to treatment will be assessed using RECIST v1.1 criteria. Tumour size, Progression Free Survival and Objective Response Rate will all be determined.

Tumour Size, will be assessed at baseline and on scans at subsequent time points and recorded as the sum of the longest diameters of the target lesions.

Progression Free Survival (PFS) is defined by the progression criteria of RECIST.

Objective Response Rate (ORR) is defined as the percentage of patients who have at least one visit response of CR or PR prior to any evidence of progression (as defined by RECIST v1.1)

The RECIST v1.1 (January 2009) guidelines for measurable, non-measurable, target and non-target lesions and the objective tumour response criteria (complete response, partial response, stable disease or progression of disease) are detailed in Appendix A

Baseline assessment should be performed no more than 28 days before the start of study treatment and ideally as close as possible to the start of study treatment; it should include all areas known for possible breast cancer metastases.

Subsequent tumour assessments will be conducted at week 6, week 12 (primary endpoint) and then every 8 weeks until objective disease progression or cessation of study treatment and finally at AZD4547 discontinuation visit. The window for each assessment is ± 1 week.

Duplicates will be made of all CT/MRI scans. These duplicate scans will be collected to enable an independent review of progression.

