8.2. Data Analysis

8.2.1. Interim Analysis

An interim analysis will occur after 20 patients are recruited into the study (including patients in the safety run in phase) and have completed their 12-week follow up. Following recommendations from the Independent Data Monitoring Committee (IDMC) data will also be reviewed once 20 patients (including patients in the safety run in phase) have completed their 20-week follow up. Recruitment into the study will continue whilst the analysis is being carried out.

$\geq 30\%$ will be considered as the 12/20-week clinical benefit rate (stable disease, partial response, complete response) of interest and $\leq 5\%$ as non-significant 12/20-week clinical benefit rate. With power of 85% and type I error of one-sided 0.05, the study will continue if 4 or more patients out of 20 show clinical benefit. If less than 4 patients show clinical benefit the study will only continue if a particular biomarker has been identified.

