8.2.8. Secondary Analyses

Frequency tabulations of the tumour response RECIST criteria and 2-category ORR will be presented.

As median time to progression is expected to be 6 months and the recruitment period to be 24 months, the analysis of PFS will take place at 30 months (when each subject has been followed up to progression or for a minimum of 6 months). At this time we anticipate that 95% of subjects will have progressed on study treatment.

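### Section 2.4 counts stable disease as objective response, against the Trial Summary, 5.2.21 and Appendix A; separately, PFS is defined throughout without death and is in fact time to progression

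*Protocol*

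**What the plan says.** **Objective response.** The protocol describes this endpoint in several places:

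- Section 2.4 (Secondary Endpoints): "Objective response rate (ORR) with 2 categories: CR, PR, SD versus PD".
- Trial Summary, Secondary Endpoints: "Objective response rate (ORR) with 2 categories: CR or PR, SD or PD".
- Section 5.2.21 (Tumour Assessments): "the percentage of patients who have at least one visit response of CR or PR prior to any evidence of progression".
- Appendix A, under Response Review, glosses objective response as CR and PR.
- Section 8.2.8 (Secondary Analyses): "Frequency tabulations of the tumour response RECIST criteria and 2-category ORR will be presented". The split is not restated.

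Section 8.2.1 (Interim Analysis) uses the three-category grouping under another name: "12/20-week clinical benefit rate (stable disease, partial response, complete response) of interest".

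**PFS.** Section 2.4 has "Progression-free survival (PFS) is time from study entry to PD (RECIST" as its definition, and the Trial Summary uses the same sentence. Section 5.2.21 adds "Progression Free Survival (PFS) is defined by the progression criteria of RECIST". None of the three names death. Section 8.2.8 sets the timing of the PFS analysis from an expected median time to progression of 6 months.

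**The concern.** Section 2.4 is the formal list of endpoints, so a programmer or report writer could reasonably take the ORR split from there. That split measures disease control. In a single-arm trial ORR has no internal comparator and is read against rates from elsewhere, where response normally means CR or PR. A rate that includes stable disease under the name ORR would look far better than it is. Section 8.2.8 does not resolve the conflict. Section 8.2.2 also colours the waterfall plot by objective response, so the ambiguity reaches a display of the primary endpoint, though not its value.

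For PFS, an endpoint with progression as its only event is time to progression. Under the name PFS, readers will assume that deaths without documented progression count as events. The protocol expects some such patients: section 8.2.2 mentions drop-out through death before the 12-week scan or progression.

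**Working it through.** The point concerns definitions, so the plan states no figure to reproduce. The passages are compared first, then the size is illustrated.

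**1. Where stable disease sits**

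| Place | Response side | Other side |
|---|---|---|
| Section 2.4 | CR, PR, SD | PD |
| Trial Summary | CR, PR | SD, PD |
| Section 5.2.21 | CR, PR before progression | all others |
| Appendix A | CR, PR | not stated |
| Section 8.2.1, as clinical benefit | SD, PR, CR | not stated |

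Section 2.4 stands alone among the descriptions of objective response and matches the clinical benefit grouping.

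**2. Size of the ORR difference**

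ORR under 2.4 − ORR under 5.2.21 = (CR + PR + SD)/n − (CR + PR)/n = SD/n.

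*Illustration from section 1.4 (Phase I study, mixed tumours):* 82 eligible patients, 1 PR, 19 with prolonged SD (8 in Parts A and B, 11 in Part C).

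- CR or PR: 1/82 = 1.2% (exact 95% CI 0.03–6.6%).
- With SD added: 20/82 = 24.4% (15.6–35.1%).
- Difference: 19/82 = 23.2 percentage points.

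*Illustration at the Phase IIa size, n = 50 (section 3.1), with assumed rates:* 5 responders (10%).

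| Assumed SD | CR or PR | 2.4 split |
|---|---|---|
| 20% (10 patients) | 5/50 = 10% | 15/50 = 30% |
| 30% (15 patients) | 5/50 = 10% | 20/50 = 40% |
| 50% (25 patients) | 5/50 = 10% | 30/50 = 60% |

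**3. Events in PFS**

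The Trial Summary, 2.4 and 5.2.21 all rest on RECIST progression alone. They agree with each other, so the question is whether the name fits the definition.

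**4. Size of the PFS difference**

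Input: the 6 months in section 8.2.8, taken as median time to progression, which is how that section words it. Assumptions: constant hazards, and deaths without prior progression forming a share d of first events. The protocol gives no value for d.

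- Progression hazard: λ = ln 2 / 6.
- Hazard of progression or death: λ / (1 − d).
- Median PFS: ln 2 × (1 − d) / λ = 6 × (1 − d).
- d = 5%: 6 × 0.95 = 5.7 months.
- d = 15%: 6 × 0.85 = 5.1 months.

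**5. Whether the data support a proper PFS**

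Section 6.3.2 records the date of death for patients who die while participating. Section 3.4 ends follow-up 28 days after the last dose. Under 5.2.21, scans continue until progression or cessation of treatment, with a final one at the discontinuation visit. A patient who stops for toxicity without progression and dies after the 28 days is therefore not captured.

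**The case against.** The strongest reply on ORR is that 5.2.21 gives an explicit definition, the Trial Summary and Appendix A agree with it, and 2.4 is a single line out of step. Section 8.2.8 also tabulates the RECIST response categories, so a reader could recover CR plus PR from the report. A SAP, promised in section 8.2.2 but not available for this review, may state the split. This is why a wrong ORR is possible and not certain. The conflict remains: a SAP would have to override one current protocol section, and that section is the endpoint list.

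On PFS, the reply is that the protocol is consistent, and that censoring rules and the handling of deaths commonly belong in the SAP. That stands as far as it goes: no contradiction can be claimed. It does not answer the mismatch of name and definition, because the protocol itself fixes the event as RECIST progression in three places.

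The Phase I illustration is also open to criticism. It rests on one PR, other tumour types and several doses, and its stable disease had to last at least 6 or 7 weeks, whereas 2.4 sets no minimum. It shows that stable disease can dominate the rate; it does not predict this trial. The n = 50 examples give a three- to six-fold ratio, so the twenty-fold Phase I ratio should not be used as a forecast.

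**Conclusion.** The ORR line in 2.4 is wrong as written. It contradicts three other places in the protocol and, if followed, overstates ORR by exactly the stable disease proportion: 20 to 50 percentage points under the assumed rates at n = 50, and 23.2 points on the Phase I counts.

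The PFS definition is consistent but badly fixed, because it describes time to progression. If the 6 months is time to progression and deaths are 5–15% of first events under constant hazards, median PFS would be about 5.7 to 5.1 months. The death share is an assumption.

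Stronger readings that the protocol does not support:

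- *That the PFS definition contradicts other sections.* The Trial Summary wording is identical, and 5.2.21 rests on the same criterion.
- *That omitting deaths would lift a 6-month median to something longer.* The 6 months is already stated without death, so counting deaths lowers it.
- *That patients who die will be censored as if still at risk.* The protocol gives no PFS censoring rule.
- *That starting PFS at study entry is an error.* Section 5.1 counts assessment days from Cycle 1 Day 1, but that does not conflict with starting PFS at entry. The definition only needs to name the date.
- *That both endpoints will be misreported.* ORR could be; the four-category table limits the damage.

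ORR is only tabulated and both endpoints are secondary. The correction is worthwhile and cheap, but it does not bear on the validity of the primary analysis, the sample size or the interim rule.

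**What to change.** **ORR.** Change the line in section 2.4 to CR or PR versus SD or PD, in agreement with the Trial Summary, 5.2.21 and Appendix A. Report CR, PR and SD together only as clinical benefit rate, the name already used in 8.2.1. State in 8.2.8 that the two-category table uses the corrected split.

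**PFS.** In the Trial Summary, 2.4 and 5.2.21, define it as time from a stated start date to the first of RECIST progression or death from any cause, and align the wording of 8.2.8. Use the death dates collected on study (6.3.2), and note that deaths after the 28-day follow-up are not captured. If the team does not want death as an event, rename the endpoint time to progression in all these places.

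**Cost.** The ORR correction takes one line in 2.4 and a clarifying phrase in 8.2.8. The PFS change takes a few lines across four sections. Neither needs new data collection if the limit on late deaths is accepted and reported; capturing those deaths would require longer follow-up. Reported ORR will be lower than under the 2.4 split, and median PFS may be somewhat shorter than time to progression.
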